9.11.1.1.6. Subsequent Pregnancies

Individuals who have previously enrolled in the registry with a prior pregnancy will be eligible to enroll in the registry, but any subsequent pregnancy will be excluded from the main analysis population if a prior pregnancy is included. Subsequent pregnancies will be included in supplementary analyses.

9.11.1.1.7. Multiple Gestation Pregnancies

Multiple gestation pregnancies will be enrolled in the registry and included in the main analysis population; however, for the analyses of preterm birth, SGA, LGA, rapid infant weight gain, postnatal growth deficiency, and infant developmental delay, multiple gestation pregnancies will be excluded from the main analysis population due to the higher risk of these outcomes in twins and higher order multiples.

9.11.2. Statistical Methods

Registry data will be summarized in tables and listings by study cohort, as appropriate. These data include maternal demographic characteristics and pre-pregnancy anthropometrics, pregnancy information, maternal obstetrical history, family history of congenital malformations, disease information, maternal exposures during pregnancy, pregnancy outcome information (including gestational age of outcome), and infant outcome information.

For each continuous variable, the number of observations, median, mean, standard deviation, minimum, and maximum will be reported. For each categorical variable, the frequency and percentage in each category will be reported. The frequency and percentage of participants with missing data for each data point will be presented. Results will be rounded to one decimal place; therefore, percentages may not always add up to 100.

Pair-wise comparisons of demographic and baseline characteristics and event rates of the outcomes of interest will be conducted between the study cohorts, as follows:

- Comparison #1: Tirzepatide exposed cohort vs. AOM active comparator cohort

- Comparison #2: Tirzepatide exposed cohort* vs. AOM unexposed comparator cohort
*Comparison #2 will include a subset of tirzepatide exposed cohort who have obesity or are overweight with at least one weight-related comorbid condition at the time of conception so as to improve comparability to AOM unexposed comparator cohort with the same obesity-related eligibility criteria.

For the analysis, participants from all countries will be pooled. Comparisons will be conducted using the methods described below, and p-values and 95% confidence intervals will be reported, as appropriate, to reflect statistical uncertainty. All outcomes will be analyzed as binary variables. The study is not powered for multiple comparisons; thus, p-values associated with secondary or exploratory outcomes will be nominal.

In addition, the prevalence of the outcomes in the general population and/or populations of individuals overweight or with obesity, from the literature, will be used to put the registry-observed outcome prevalences into context.

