This study will collect data from participants and HCPs involved in their care or the care of their infants via concise data collection forms at pre-defined timepoints during pregnancy, at pregnancy outcome, and up to 1 year of infant age.

Study size

The study aims to include a minimum of 364 pregnant individuals in each cohort to estimate the prevalence of the primary outcome, MCM, with meaningful confidence and precision and detect a 3-fold increase in the tirzepatide-exposed cohort compared to the AOM active comparator and AOM unexposed comparator cohorts.

Data analysis

Pair-wise comparisons of demographic and baseline characteristics and event rates of the outcomes will be conducted between the study cohorts, as follows:

- Comparison #1: Tirzepatide exposed cohort vs. AOM active comparator cohort
- Comparison #2: Tirzepatide exposed cohort* vs. AOM unexposed comparator cohort
 - *Comparison #2 will include a subset of the tirzepatide exposed cohort who have obesity or are overweight with at least one weight-related comorbid condition at the time of conception so as to improve comparability to AOM unexposed comparator cohort with the same obesity-related eligibility criteria.

The prevalence of each outcome will be calculated by dividing the number of cases of the outcome by the appropriate denominator for that particular outcome, along with 95% confidence interval (CI). For most outcomes, the analysis population (denominator) will be the number of pregnant individuals, number of pregnant individuals with pregnancy outcome data, the number of live births, or the number of infants with follow-up data at the time point of interest, as appropriate; however, for some outcomes, the analysis population (denominator) will be restricted based on certain relevant factors.

Formal quantitative comparisons of the event rates of the outcomes of interest will be conducted between the tirzepatide exposed and each of the two comparator cohorts. For each outcome, if

the number of events permits, results will be presented for both unadjusted and adjusted models. Summary statistics (relative risk) will be reported along with their 95% CIs and p-values. Adjusted methods will incorporate weights estimated using the stabilized inverse probability of treatment weighting (IPTW) method to balance the cohorts regarding observable covariates. Where sample size permits, subgroup analyses will be conducted considering the timing and extent of exposure.

Milestones

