9.9. Study Size

9.9.1. Sample Size

Table 9.4 presents by outcome the sample size (number of live births or pregnant individuals, depending on the outcome) required in each cohort to detect a range of relative risks, from 1.5 to 5.5. Sample size calculations were performed with SAS® statistical software (version 9.4 or higher, SAS Institute, Cary, NC) for the outcomes using the Fisher's exact conditional test with Walters normal approximation method, and assuming a power of 80%, a 2-sided α level of 0.05, an equal number of individuals in each cohort (although other sampling ratios were considered), and observed prevalence of the outcomes in the comparator cohort equivalent to reference rates in the general population. These general population rates were obtained for most (but not all) of the outcomes from various sources, including the Metropolitan Atlanta Congenital Defects Program (MACDP), the National Vital Statistics System (NVSS), and published literature.

Although the registry aims to examine a variety of maternal, fetal, and infant outcomes, the target sample size for the registry is based on the primary outcome, overall prevalence of MCM, which also is the outcome with the most restrictive denominators and one of the lowest prevalence in the general population.

As shown in Table 9.4, 265 live births in the analysis population of each cohort are needed to detect a 3-fold increase in the overall prevalence of MCM between cohorts, or a relative risk of 3.

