To estimate the number of pregnant individuals who will need to be enrolled to result in 265 live births per cohort, several factors were considered, including the expected registry live birth rate, the proportion of enrolled individuals expected to be exposed to tirzepatide in the first trimester, and the proportion of enrolled individuals expected to be excluded from the analysis population. It was assumed that 90% of enrolled individuals would be exposed in the first trimester, 90% of enrolled pregnancies would result in a live birth,^{72,73} and 10% of enrolled individuals would be excluded from the analysis population due to the occurrence of pregnancy outcome prior to enrollment (retrospectively enrolled participants), exposure to a known teratogen or an investigational medication or congenital infectious agents during pregnancy (teratogen/investigational medication/congenital infectious agent-exposed participants), lack of pregnancy outcome data (participants lost to follow-up; assumed to constitute 5%), or inclusion of a prior pregnancy in the analysis population (subsequent pregnancies). These assumptions are based on experience with other similar study designs. To ensure adequate sample size in the main analysis population is achieved, enrollment of the main analysis population will be assessed throughout data collection. If higher than anticipated percentages of participants would be excluded from the analysis population, it will be assessed what (if any) potential mitigations should be implemented. It is also acknowledged that there could be some effective sample size loss due to the use of stabilized IPTW. The extent and potential mitigations for this will be assessed after approximately 100 participants have enrolled in each of the cohorts.

Given these assumptions, to attain 265 live births per cohort, 364 (=265/0.9/0.9/0.9) pregnant individuals would need to be enrolled in each of the three cohorts of the study population, and a

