total of 1,092 individuals would need to be enrolled in the registry. This sample size will afford the study the ability to detect a 3-fold increase in the overall prevalence of the primary outcome, MCM, in the tirzepatide-exposed cohort, with meaningful confidence (95% confidence level). Additionally, [Table 9.5](#) shows that, without any adjustments for multiple comparisons, the proposed sample size will also afford the study >80% power to detect a 3-fold increase in several of the secondary and exploratory outcomes.

The overall prevalence of MCM is higher among individuals with obesity (BMI >30 kg/m²; 3.9%²⁶) than that of the general population (3%).⁷⁴ However, because it is difficult to estimate the proportion of enrolled individuals who will have obesity at the time of conception (as some will have lost weight prior to conception due to weight management treatment), the more conservative approach assuming an overall prevalence of 3% has been chosen (i.e., the overall sample size calculations were based on the general population prevalence of MCM). Had the higher rate (3.9%) been used, the total sample size for the registry would have been substantially lower (828 vs. 1092). These assumptions also may be re-evaluated after interim analyses have been conducted.

Table 9.4. Sample Size Needed per Cohort to Detect Specific Relative Risk (Exposed: Tirzepatide Unexposed^c)

Outcomes ^a	Reference Prevalence in Unexposed Group	Reference	Denominator of Reference	RR= 1.5	RR= 2.0	RR= 2.5	RR= 3.0	RR= 3.5	RR= 4.0	RR= 4.5	RR= 5.0	RR= 5.5
Primary Objective												
MCM	3.0%	CDC 2008 ⁷⁴	Live births	2,627	796	413	265	190	146	117	97	82
Secondary Objectives												
Pre-eclampsia	3.8%	Ananth 2013 ⁷⁵	Pregnant individuals	2054	622	322	206	148	113	91	75	64
Eclampsia	0.281%	Butwick 2020 ⁷⁶	Live births	28973	8824	4600	2961	2130	1640	1322	1101	940
Gestational diabetes	6.9%	Martin 2021 ⁷⁷	Pregnant individuals	1161	350	180	115	82	62	50	41	35
Pregnancy-induced hypertension	6.5%	Butwick 2020 ⁷⁶	Pregnant individuals	1088	327	169	107	76	58	46	38	32
SAB	11.8%	Wu 2019 ⁷⁸	Pregnant individuals	596	177	90	57	40	30	24	19	16
Stillbirth	0.596%	MacDorman 2015 ⁷⁹	Live births and stillbirths	13610	4142	2159	1389	999	769	619	516	440
Induced abortion	18.6%	Jatlaoui 2019 ⁸⁰	Live births	343	100	50	31	21	15	12	9	NA ^b
Preterm birth	8.47%	Martin 2021 ⁷⁷	Singleton live births	868	260	134	85	60	46	36	30	25
SGA	10.0%	By definition	Live births	721	215	110	70	49	37	29	24	20

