Postnatal growth deficiency	10.0%	By definition	Live births	721	215	110	70	49	37	29	24	20
Infant developmental delay	13%	Rosenberg 2008 ⁸¹	Live births	532	158	80	50	35	26	21	17	14
Exploratory Objectives												
Heart Failure	0.12%	Mogos 2018 ⁸²	Pregnant individuals	667975	20706	10798	6952	5002	3853	3107	2588	2210

Outcomes ^a	Reference Prevalence in Unexposed Group	Reference	Denominator of Reference	RR= 1.5	RR= 2.0	RR= 2.5	RR= 3.0	RR= 3.5	RR= 4.0	RR= 4.5	RR= 5.0	RR= 5.5
Peripartum Cardiomyopathy	0.03%	Harper 2012 ⁸³	Live births	272189	82925	43251	27847	20039	15437	12450	10374	8858
Hyperemesis gravidarum	2.5% (0.3 to 3.5%)	ACOG 2015 ⁸⁴	Pregnant individuals	3171	962	500	321	230	176	142	118	100
Inadequate GWG	15% (12 to 25%)	CDC 2015 ⁸⁵	Pregnant individuals	448	132	67	42	29	22	17	13	11
LGA	10.0%	Hocquette 2021 ⁸⁶	Live births	721	215	110	70	49	37	29	24	20
Rapid infant weight gain	8% (5 to 14%)	Eckhardt 2016 ⁸⁷	Live births	925	278	143	91	64	49	39	32	27

Abbreviations: GWG = gestational weight gain; MCM = major congenital malformation; NA = not available; reference prevalence = prevalence of outcome in general population for pregnant individuals of any age; RR = relative risk; SAB = spontaneous abortion; SGA = small for gestational age.

^a Only outcomes with published reference rates in the general population are included in the table.

^b For induced abortion, an RR of 5.5 with a reference rate of 18.6% in the unexposed cohort would result in a rate above 100% in the exposed cohort.

^c Sampling ratio is 1:1 (Exposed: Tirzepatide Unexposed). Comparisons between tirzepatide exposed vs. AOM active comparator and tirzepatide exposed vs. AOM unexposed comparator will be conducted separately.

Notes: Sample size calculations were performed in SAS (version 9.4) for the outcomes using Fisher's exact conditional test with Walters normal approximation method, and assuming a power of 80% and a 2-sided α level of 0.05.

Table 9.5. Power to Detect a 3-fold Increase, by Study Outcome

Outcomes	Power Estimate
MCM	80%
Pregnancy-induced hypertension	>80%
Pre-eclampsia	>80%
Eclampsia	5.9%
Gestational diabetes	>80%
Heart failure	0%
Peripartum Cardiomyopathy	0%
Hyperemesis gravidarum	71.5%
Inadequate maternal weight gain	>80%
SAB	>80%
Stillbirth	21.4%
Induced abortion	>80%
Preterm birth	>80%
SGA	>80%
LGA	>80%
Postnatal growth deficiency	>80%
Rapid infant weight gain	>80%
Infant developmental delay	>80%

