9.11.1. Definition of Analysis Sets

9.11.1.1. Analysis Population

As depicted in [Figure 9.2](#), the main analysis population will include participants who:

- Are valid (Section 9.11.1.1.1)
- Had a qualifying diagnosis at the time of prescribing (Section 9.11.1.1.2)
- Are prospectively enrolled (Section 9.11.1.1.3)
- Are not exposed to teratogens or investigational medications or congenital infectious agents during pregnancy (Section 9.11.1.1.4)
- Are not considered lost to follow-up (Section 9.11.1.1.5)
- Are not already included in the analysis population for a prior pregnancy (Section 9.11.1.1.6), and
- Among the tirzepatide exposed cohort, have not been exposed to other GLP-1 RA therapies during pregnancy or within 5 times the half-life of the drug prior to conception.

For the analyses of preterm birth, SGA, postnatal growth deficiency, rapid infant weight gain, and infant developmental delay, multiple gestation pregnancies will be excluded from the analysis population.

Abbreviation: HCP = healthcare professional; GLP-1 RA = glucagon-like peptide-1 receptor agonist.

Figure 9.2. Attrition diagram.

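### The 80% power for a 3-fold MCM increase is not secured for Comparison #2, because the 364-per-cohort figure has no allowance for its BMI-at-conception subset; some entries in Tables 9.4 and 9.5 also need correcting

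*Protocol*

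**What the plan says.** Section 9.9.1 sizes the registry on major congenital malformations (MCM): 3% prevalence in the comparator, relative risk 3, "assuming a power of 80%, a 2-sided α level of 0.05, an equal number of individuals in each cohort", and "using the Fisher's exact conditional test with Walters normal approximation method". This gives 265 live births per cohort. The inflation to enrolled numbers is "364 (=265/0.9/0.9/0.9) pregnant individuals would need to be enrolled in each of the three cohorts of the study population". The three factors are first-trimester exposure, live birth, and exclusion from the analysis population. The reasons listed for the 10% exclusion are retrospective enrolment, teratogen, investigational-drug or congenital-infection exposure, loss to follow-up, and subsequent pregnancy.

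The Abstract (Study size) applies the result to both comparators: the study is to "detect a 3-fold increase in the tirzepatide-exposed cohort compared to the AOM active comparator and AOM unexposed comparator cohorts".

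Section 9.11.2 narrows one of these comparisons: "Comparison #2 will include a subset of tirzepatide exposed cohort who have obesity or are overweight with at least one weight-related comorbid condition" at conception. Section 9.7.2 says the same. Section 9.9.1 recognises that treatment may move people out of this group, noting that "it is difficult to estimate the proportion of enrolled individuals who will have obesity at the time of conception". It uses that only to choose 3% over the 3.9% reported for obesity.

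Section 9.11.1.1 adds a further condition for the main analysis population: "Among the tirzepatide exposed cohort, have not been exposed to other GLP-1 RA therapies during pregnancy" or within five half-lives before conception. The 10% allowance does not list it.

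Table 9.5 gives power by outcome (80% for MCM, 71.5% for hyperemesis gravidarum, 21.4% for stillbirth) without stating the sample size behind each figure.

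**The concern.** Both adjusted MCM comparisons are primary, and footnote c of Table 9.4 says they are run separately. If the tirzepatide arm of Comparison #2 is smaller than the sizing assumes, the stated power is too high for that comparison. The effect would be specific to the comparison with untreated pregnancies, and it falls on the arm that is hardest to recruit: Section 9.9.2 projects 305 exposed pregnancies in ten years against a target of 364. At stake is how a non-significant result against the unexposed cohort is read. The error in Table 9.5 matters less, because those outcomes are secondary or exploratory with nominal p-values, but the table is the protocol's only statement of what the study can detect for them.

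**Working it through.** **Reproducing the plan.** Walters approximation, two-sided 5%, comparator (n1, p1) and exposed (n2, p2):

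power = Φ{ 2√[n1·n2/(n1+n2)] × [asin√(p2 − 1/(2·n2)) − asin√(p1 + 1/(2·n1))] − 1.96 }

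With n1 = n2 = 265, p1 = 0.03, p2 = 0.09: 23.02 × (0.3014 − 0.1795) − 1.96 = 0.845, so power = 80.1%. The formula returns the MCM entries 2,627, 796, 413 and 265 of Table 9.4 for relative risks 1.5 to 3. Then 265/0.729 = 363.5, rounded up to 364. At 3.9% it gives 201 live births, 276 enrolled per cohort and 828 in total, as the protocol states. The plan's figures reproduce, with no slack at 3%.

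**Comparison #2.** Assumption: a share s of the 265 tirzepatide live births meets the BMI criterion at conception. The documents give no value, so a range is shown. The unexposed arm is taken as 265, or as 364 × 0.9 × 0.9 ≈ 295, because Table 9.6 applies the first-trimester restriction only to exposed cohorts. Example for s = 70% (186 live births) against 265: 20.91 × (0.29996 − 0.1795) − 1.96 = 0.558, so power = 71.2%.

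| Share retained | Tirzepatide live births | Walters 3%, 265 unexposed | Walters 3%, 295 unexposed | Exact Fisher 3%, 295 unexposed | Walters 3.9%, 265 unexposed |
|---|---|---|---|---|---|
| 100% | 265 | 80.1% | 82.4% | 85.2% | 90.7% |
| 90% | 238 | 77.6% | 80.0% | 83.2% | 89.0% |
| 80% | 212 | 74.8% | 77.0% | 80.8% | 86.8% |
| 70% | 186 | 71.2% | 73.4% | 76.8% | 84.0% |
| 60% | 159 | 66.5% | 68.5% | 74.6% | 80.0% |
| 50% | 132 | 60.4% | 62.3% | 70.7% | 74.5% |

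At 3% by Walters, power falls below 80% with almost any loss when 265 are unexposed, and at about 90% retention when 295 are. At 3.9% it does so only below about 60%.

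**Table 9.5.** In Table 9.7, hyperemesis and stillbirth share one denominator, the individuals in the analysis population: 364 × 0.9 ≈ 328.

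| Outcome (reference rate) | Table 9.5 | n = 265: Walters / exact | n = 328: Walters / exact | n = 364: Walters / exact |
|---|---|---|---|---|
| Hyperemesis (2.5%) | 71.5% | 70.9 / 71.5% | 81.1 / 81.2% | 85.4 / 85.5% |
| Stillbirth (0.596%) | 21.4% | 13.9 / 11.0% | 18.6 / 16.4% | 21.3 / 19.4% |

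The hyperemesis figure fits 265 and the stillbirth figure fits the enrolled 364, so the table uses different sample sizes for the same denominator. At 328 hyperemesis has about 81%, as it should when Table 9.4 requires 321 for 80%.

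**Table 9.4.** For relative risks 1.5, 2, 2.5 and 3, Walters gives 1,088, 327, 169 and 107 at 6.9%, and 1,161, 350, 180 and 115 at 6.5%. The table prints the second series for gestational diabetes (6.9%) and the first for pregnancy-induced hypertension (6.5%). The two rows are transposed.

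**The case against.** A reader might infer that the 80% power simply fails for Comparison #2. The documents do not support that. They give no retained share, and everyone in Comparison #2 has obesity, or overweight with a comorbidity, at conception, so the 3.9% rate is arguably nearer than 3%. At 3.9% a substantial loss can be absorbed. This stands and makes the shortfall conditional. It does not remove the gap: the protocol sizes on 3%, and 3.9% is a rate for obesity, so a comparison containing overweight participants may sit between the two.

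A reader might also take the 20.9% weight loss in Section 7.4.3 as showing that most users would leave the subset. That figure belongs to week 72 at one dose level. Cohort entry requires a single dose, and no treatment duration before conception is assumed, so it cannot supply the retained share.

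Monitoring is planned. Section 9.9.1 will track enrolment of the main analysis population and consider mitigation, assumptions may be revisited after interim analyses, 364 is a minimum, and the propensity-score check at about 100 per cohort treats the comparisons separately. This is a real safeguard, but no step names the subset share. The variance inflation factor in Section 9.11.2.4 is the ratio of actual to effective sample size, so it measures loss from weighting, not loss from restriction.

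Other possible omissions from the 10% allowance are weaker. Invalid participants and users for other indications can be read as never counting towards a cohort's 364. Only other GLP-1 RA exposure is a clear omission. The 5.9% for eclampsia in Table 9.5 lies between the Walters values at 265 (4.7%) and 328 (6.5%) and is not shown to be wrong. The transposed rows change nothing in Table 9.5, since 107 and 115 are both far below 265.

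**Conclusion.** The calculation omits a restriction that the protocol itself places on a primary comparison, while the Abstract claims 3-fold detection against both comparators without qualification. Power for Comparison #2 is unsecured rather than shown to be inadequate. Across retained shares of 90% to 50% at 3%, it runs from 78% to 60% by Walters with 265 unexposed live births, and from 83% to 71% by exact Fisher with 295. At 3.9% by Walters with 265 unexposed, it runs from 89% to about 74%, reaching 80% near 60% retention. These figures rest on an assumed share and on the plan's other factors holding, and they include no loss from weighting. The hyperemesis entry in Table 9.5 is about 10 points too low. The stillbirth entry is about 3 points too high by Walters, or 5 by the exact test. The Table 9.4 transposition is a plain error without consequence for the design.

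**What to change.** - In Section 9.9.1 and the Abstract, replace the unqualified claim for both comparisons with Comparison #2 power over a range of assumed retained shares (for example 50% to 90%), at both 3% and 3.9%.
- Add other GLP-1 RA exposure to the reasons covered by the 10% allowance. It affects the tirzepatide cohort in both comparisons.
- At the 100-per-cohort check, report the observed retained share for Comparison #2 beside its variance inflation factor.
- Recompute Table 9.5 with one stated method on each outcome's own Table 9.7 denominator, and show the sample size used.
- Swap the gestational diabetes and pregnancy-induced hypertension sample-size rows in Table 9.4.

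The cost is restated text and figures, with one extra number at a check that is already planned. No added enrolment is proposed. The drawback for the sponsor is a less favourable, conditional power statement for Comparison #2.
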